### SP analysis groups

The SP analysis groups are defined according to the treatment regimen and patient's fibrosis status. The standard summaries by SP groups in the safety population are as follows (if not specified otherwise):

- Total (regardless of cirrhosis status)
  - (1) Total
  - (2) 2DAA w/o RBV
  - (3) 2DAA + RBV
  - (4) 3DAA w/o RBV
  - (5) 3DAA + RBV
- Patients with cirrhosis
  - (6) Total
  - (7) 2DAA w/o RBV
  - (8) 2DAA + RBV
  - (9) 3DAA w/o RBV
  - (10) 3DAA + RBV
- Patients without cirrhosis
  - (11) Total
  - (12) 2DAA w/o RBV
  - (13) 2DAA + RBV
  - (14) 3DAA w/o RBV
  - (15) 3DAA + RBV
- Patients with unknown fibrosis status
  - (16) Total
  - (17) 2DAA w/o RBV
  - (18) 2DAA + RBV
  - (19) 3DAA w/o RBV
  - (20) 3DAA + RBV

(2DAA - paritaprevir/r-ombitasvir, 3 DAA - paritaprevir/r-ombitasvir + dasabuvir, RBV – ribavirin taken, w/o RBV – no ribavirin taken)

**NCP analysis groups**

The summary tables for the NCP will only show the data pooled for all patients in the NCP without any subgrouping by genotype and/or fibrosis status.

**4.2.2 Definition of Baseline and Visit Time Windows**

This observational study covers three documentation periods, see Figure 1. An overview of data to be collected throughout the study is summarized in Table 3.

**Table 2 - Data Documentation Schedule**

Assessment/ Procedure (only available data to be collected; no diagnostic or monitoring procedures to be applied to the patients apart from those of routine clinical practice)	Baseline	Treatment Period			Post-treatment (PT) Period		
		On-treatment visits	Mid treatment visit for pts receiving 24 weeks of therapy	EoT b	Early PT visit	SVR 12 visit	SVR 24 visit
Patient authorization	X a						
Demographic information	X						
IL28B	X						
Relevant CHC disease characteristics	X						
Liver fibrosis stage	X					X	X
CHC treatment history	X						
HCV genotype and subtype	X						
HCV RNA samples	X	X	X	X	X	X	X
Clinical chemistry and hematology	X	X	X	X	X	X	X
ABBVIE REGIMEN initiation documentation	X						
ABBVIE REGIMEN adherence		X	X	X			
Concomitant medication	X	X	X	X			
Relevant medical history, co-morbidities	X						
sAE, AE and pregnancy reporting	X	X	X	X	X c	X d	X d
For patients receiving RBV: Evidence, in accordance with local label, that female patient or female partner of male patient is not pregnant	X						
Patient questionnaires – FACIT-F	X	X	X	X		X	X
Patient questionnaires – WPAI	X			X		X	X
Patient questionnaires – PRISM	X					X	X
Patient questionnaires – PAM-13	X			X			

Abbreviations: EoT = End of Treatment (at Week 12 or 24 or at premature discontinuation),  
PT = Post-Treatment

- a Written patient authorization must be obtained before any data documentation in the eCRF
- b Patients who prematurely discontinue should return to the site to document EoT data
- c Tolerability documentation until PT week 4
- d Pregnancy reporting for patients treated with DAA plus RBV

In accordance with the non-interventional nature of the study all HCV RNA measurements will be performed at the sole discretion of the physician and all HCV RNA measurements have to be entered into the eCRF. All recorded HCV RNA values will be assigned to appropriate time points (baseline, on-treatment visits, EoT visit, post-treatment visits) as follows:

**Table 3 - Analysis Time Windows for HCV RNA**

Phase	Time point	Time Window
Pre-Treatment	Baseline	Last value prior to start of study treatment (i.e. $\leq$ study day 1)
On-treatment		Study day during treatment period^# (Study day 1 = first treatment day)
Treatment Week	4 (RVR*)	15 - 42^
EoT	Actual EoT	Study day of last dose# (28 days prior to last dose - 7 days post last dose)
Post Treatment	12 weeks (SVR 12 window)	$\geq$ 70-126 days post last dose
	24 weeks (SVR24 window)	127-210 days post last dose
	48 weeks (SVR48 window)	> 210 days post last dose

^values must also be  $\leq$  7 days post last dose

#  $\geq$ study day 2

\*RVR = rapid virological response

All reported safety laboratory test results will be assigned to one of the time points using the time windows specified in the table below.

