#### 4.1.2 Secondary Parameters

The secondary effectiveness endpoints are:

- The percentage of patients with virological response (HCV RNA  $< 50$  IU/mL) at EoT (defined as last intake of ABBVIE REGIMEN or ribavirin)
- The percentage of patients with relapse (defined as HCV RNA  $< 50$  IU/mL at EoT followed by HCV RNA  $\geq 50$  IU/mL)
- The percentage of patients with breakthrough (defined as at least one documented HCV RNA  $< 50$  IU/mL followed by HCV RNA  $\geq 50$  IU/mL during treatment).
- Rapid virological response at week 4 (RVR 4, i.e. patients with HCV RNA  $< 50$  IU/mL at week 4)
- Sustained virological response 24 weeks after EoT (SVR24, i.e. patients with HCV RNA  $< 50$  IU/mL 24 weeks after EoT)
- Sustained virological response 48 weeks after EoT (SVR48, i.e. patients with HCV RNA  $< 50$  IU/mL 48 weeks after EoT)
- The number and percentage of patients meeting each and any of the following SVR12 non-response categories:
  - On-treatment virologic failure (breakthrough [defined as above] or failure to suppress [each measured on-treatment HCV RNA value  $\geq 50$  IU/mL])
  - Relapse (defined as HCV RNA  $< 50$  IU/mL at EoT followed by HCV RNA  $\geq 50$  IU/mL post-treatment for subjects who complete treatment [not more than 7 days shortened])
  - Premature study drug discontinuation with no on-treatment virologic failure

- Missing SVR12 data and/or none of the above criteria

Further secondary variables are:

- Type of treatment regimen ( $\pm$  Dasabuvir,  $\pm$  RBV, intended and actual combination, dose and duration)
- Adherence
  - Percentage of the DAA dose taken in relation to the target dose of DAA (cumulative dose taken divided by target dose in percent)
  - Percentage of the RBV dose taken in relation to the target dose of RBV (cumulative dose taken divided by target dose in percent)
  - Percentage of missed RBV treatment days in relation to the target number of RBV treatment days
- Co-morbidities and concomitant medication
- Serious and non-serious adverse events and pregnancy occurrences
- Questionnaires on PROs: e.g. PAM-13, FACIT-Fatigue, PRISM and work productivity and activity impairment (WPAI) questionnaire prior to treatment initiation, at EoT as well as 12, 24 and 48 weeks after EoT

No data will be imputed for any effectiveness or safety analyses except for the analyses of the HCV RNA endpoints and PRO questionnaires (if applicable). For further details see sections 4.2.3 and 4.2.7.2.3, respectively.

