**Table 4 - Analysis Time Windows for Safety Laboratory Data**

Phase	Time point	Time Window
Pre-Treatment	Baseline	Last value prior to start of study treatment (i.e. $\leq$ study day 1)
Treatment Weeks	4 (day 29)	Study day during treatment period (Study day 1 = first treatment day)
	8 (day 57)	15 – 42 ^
	12 (day 85)	43 – 70 ^
	16 (day 113)	71 – 98 ^
EoT	Actual EoT	Study day of last dose# (28 days prior to last dose - 7 days post last dose)
Post Treatment	4 weeks (28 days post last dose)	8– 56 post last dose
	12 weeks (84 days post last dose)	57 – 126 days post last dose
	24 weeks (168 days post last dose)	127 – 252 days post last dose
	48 weeks (336 days post last dose)	253 – 420 days post last dose

^values must also be  $\leq$  7 days post last dose

#  $\geq$ study day 2

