#### 4.2.3 Handling of missing data

No data will be imputed for any effectiveness or safety analyses except for the analyses of the HCV RNA endpoints and certain PRO endpoints. The discussion of missing data imputation for the PRO endpoints is included in section 4.2.7.2.3.

HCV RNA values will be selected for an RVR, EOTR and SVR analysis based on visit windows as defined in Table 4. When there is no HCV RNA value in a visit window based on defined visit windows, the closest values before and after the window, regardless of the value chosen for the subsequent and preceding window, will be used for the flanking imputation described below. For analysis of RVR, EOT and SVR, if a subject has a missing HCV RNA value at a post-Day 1 visit but with undetectable or unquantifiable (LLoD or LLoQ  $\leq$ 50 IU/mL) HCV RNA levels at both the preceding value and succeeding value, the HCV RNA level will be considered undetectable or unquantifiable, respectively, at this visit for this subject. In addition, if a subject has an

unquantifiable HCV RNA level at the preceding value and an undetectable HCV RNA level at the succeeding value, or vice versa, the HCV RNA level will be imputed as unquantifiable at this visit for this subject.

For analyses of RVR, subjects still missing a value for the visit after flanking imputation will be considered as a failure. For EoTR and SVR analysis, if there is no value in the appropriate window after flanking imputation but there is an HCV RNA value after the window, then it will be imputed into the EoTR or SVR window respectively. Subsequent to this flanking and backward imputation, if the HCV RNA value remains missing at a specific time point, then the subject will be considered as virological failure at this time point (i.e., not undetectable or unquantifiable).

If a subject starts another treatment for HCV, then all HCV RNA values for this subject measured on or after the start date of the new HCV treatment will be excluded from analyses. The subject will be considered a failure for summaries of viral response at all time points after the start of the new HCV treatment.

Due to the non-interventional nature of this study several different methods for determination of the HCV RNA value can be applied. For the purpose of the statistical analysis, a HCV RNA measurement is considered <50 IU/mL,

- if a PCR test was used

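### The SVR48 window opens at day 211, just after week 30, so a responder last sampled 84 to 125 days before week 48 can be reported as sustained at week 48

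*SAP*

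**What the plan says.** SAP 4.1.2 lists as a secondary endpoint "Sustained virological response 48 weeks after EoT", meaning HCV RNA below 50 IU/mL at that time.

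SAP Table 3 sets the HCV RNA windows. Week 24 is "127-210 days post last dose" and week 48 is "> 210 days post last dose", with no closing day.

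SAP 4.2.1 admits a patient to CPSFU48 on evaluable HCV RNA more than 210 days after the last dose. A patient can also enter with a last post-baseline value of at least 50 IU/mL, or if later data are missing for safety or virologic-failure reasons. SAP 4.2.7.2.1 reports SVR48 in that population.

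SAP Table 4, for safety laboratory data, gives the nominal day as "48 weeks (336 days post last dose" and uses different boundaries: "127 – 252 days post last dose" for week 24 and "253 – 420 days post last dose" for week 48. Table 4 in protocol 9.7.4 has the same two windows.

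For an empty window, SAP 4.2.3 first applies flanking imputation from the nearest values on either side. If that fails and "there is an HCV RNA value after the window, then it will be imputed into the EoTR or SVR window respectively".

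Protocol 9.7.1 leaves the HCV RNA windows to the SAP. Protocol 9.3.2 lists relapse or reinfection after SVR12, up to post-treatment week 48, as a secondary variable.

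**The concern.** The label and the window disagree. A blood sample drawn on day 215 counts as week 24 for ALT and as week 48 for HCV RNA. HCV RNA testing is left to the physician's routine, so a week-24 visit that slips by a little over six weeks becomes a week-48 result.

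The population rule has the same problem. A responder lost for unrelated reasons after a sample on day 205 is left out of CPSFU48. The same patient lost after a sample on day 215 is counted as a week-48 success.

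SVR48 is the study's statement on durability. A reader will take it to mean that patients were observed to be virus-free about 48 weeks after treatment. For patients last sampled on days 211 to 252 that was not observed.

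**Working it through.** **Inputs.** SVR24 and SVR48 windows from SAP Table 3; laboratory windows and nominal day from SAP Table 4; CPSFU rules from SAP 4.2.1; imputation rules from SAP 4.2.3. The documents give no sample size or precision for SVR48, no late relapse or reinfection rate, and no expected distribution of sampling days.

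**The plan's own figure.** 48 × 7 = 336, which agrees with SAP Table 4. Likewise 24 × 7 = 168.

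**Position of the boundary.**
- 210 / 7 = 30.0 weeks, so the first day that counts as week 48 is day 211.
- Distance from day 211 to week 24: 211 − 168 = 43 days. To week 48: 336 − 211 = 125 days (17.9 weeks).
- Midpoint of the two targets: (168 + 336) / 2 = 252, which is the boundary in the laboratory table.
- Days 211 to 252 are 42 days assigned to week 48 for HCV RNA and to week 24 for laboratory data. Time unobserved before day 336 runs from 336 − 252 = 84 to 336 − 211 = 125 days.

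**Applying the SAP 4.2.3 rules to example histories** (days after last dose):
- Below 50 IU/mL on days 0, 84 and 215: SVR48 is yes from day 215. SVR24 is yes by flanking between days 84 and 215.
- Below 50 on days 0 and 215 only: SVR12, SVR24 and SVR48 are all yes, and the day-215 sample supports all three.
- Below 50 on days 0 and 84, at least 50 on day 215: SVR48 is no. SVR24 is also no, by backward imputation.
- Below 50 on days 0, 84 and 168, then nothing: no SVR48 value. Nothing lies beyond an open-ended window, so imputation cannot fill it. The patient leaves CPSFU48 if the reason is unrelated to safety or effectiveness.

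**Illustrative size.** Possible overstatement = f × (1 − exp(−r × g / 365.25)), where f is the share of SVR48 responders judged on the early sample, r the late relapse or reinfection rate per person-year, and g the days from sample to day 336. Both f (10% to 100%) and r (0.005 to 0.05) are assumptions.

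| | Sample on day 211 (g = 125) | Sample on day 253 (g = 83) |
|---|---|---|
| f = 10%, r = 0.005 | 0.02 points | 0.01 points |
| f = 50%, r = 0.01 | 0.17 points | 0.11 points |
| f = 100%, r = 0.05 | 1.70 points | 1.13 points |

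**The case against.** Day 210 is not arbitrary. Table 3 closes SVR12 at 84 + 42 = 126 and SVR24 at 168 + 42 = 210, so both end six weeks after target. The protocol gives the SAP authority over these windows, and nothing in the documents makes the laboratory boundary binding for HCV RNA. This explains where SVR24 ends. It does not explain why week 48 begins on the next day: the same six weeks before day 336 would be day 294 (336 − 42).

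Three stronger readings are tempting, and the documents do not support them.
- *A reader might infer that imputation inflates SVR48.* It does not. Carrying a value into the SVR24 window changes SVR24 only, and a late positive carried back lowers it. For a responder with an earlier negative value, flanking fills the gap. Reuse of a value already chosen for a neighbouring window is an explicit rule in SAP 4.2.3, and barring it would be a preference. Reuse does mean that SVR24 and SVR48 may rest on the same sample, so they are not always separate evidence.
- *A reader might infer that relapse after week 30 is lost.* SAP 4.2.7.2.1 reports late relapse, after the SVR24 window, as its own category, and all HCV RNA results must be entered. What stays unseen is relapse in patients never sampled again, and no choice of window reveals that.
- *A reader might infer that SVR48 is overstated.* Forces act in both directions. CPSFU48 keeps patients whose last value is at least 50 IU/mL and drops responders lost for unrelated reasons, and the open upper end admits positives after week 48. The SAP does not say which of several values after day 210 counts. If it is the last, as the protocol specifies for SVR12, later positives are captured.

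It also stands that SVR48 is a descriptive secondary rate with no test attached, and that a day-253 start still leaves up to 83 days unobserved.

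**Conclusion.** The mismatch is real. SVR48 is worded as a week-48 result, but Table 3 and CPSFU48 accept any sample after week 30, and the SAP places 42 of those days at week 24 for laboratory data. A responder last sampled on days 211 to 252 is reported as sustained at week 48 with 84 to 125 days unobserved.

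The rate can therefore overstate week-48 response. Whether it does so on balance, and by how much, cannot be settled from the documents. The 0.02 to 1.70 points shown above rest wholly on assumed event rates and sampling shares and leave out the opposing forces. The SVR12 window is not touched. The correction is worth making because it is cheap and makes the reported rate match its label, even though a large bias has not been shown.

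**What to change.** In the SAP:
1. Set the HCV RNA windows in Table 3 to days 127-252 for SVR24 and 253-420 for SVR48, as in the laboratory table.
2. In the CPSFU48 definition, replace more than 210 days with more than 252 days throughout.
3. State that the last value in the SVR48 window is used. Continue to report any HCV RNA of at least 50 IU/mL after day 420 as late relapse or reinfection.
4. Report the distribution of actual SVR48 sampling days, and the number of SVR24 results that rest on a sample from the SVR48 window.
5. Correct the pointer in 4.2.3, which cites Table 4 for the HCV RNA windows. Table 3 is evidently meant, since the SAP's table references generally run one number too high.

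The flanking and backward imputation rules can stay.

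Cost: wording only, with fewer patients in CPSFU48 and a slightly wider SVR48 interval. SAP Table 1 gives the scale: at a 95% rate, going from 620 to 590 patients widens the interval from 3.5 to 3.6 points. The SVR24 window would reach 84 days past its target (252 − 168). Responders last seen on days 211 to 252 and lost for unrelated reasons would leave CPSFU48, while patients whose last value on those days is positive would stay. This is a further reason to show the sampling days beside the rate.

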**Table 4 - Analysis Time Windows for Safety Laboratory Data**

Phase	Time point	Time Window
Pre-Treatment	Baseline	Last value prior to start of study treatment (i.e. $\leq$ study day 1)
Treatment Weeks	4 (day 29)	Study day during treatment period (Study day 1 = first treatment day)
	8 (day 57)	15 – 42 ^
	12 (day 85)	43 – 70 ^
	16 (day 113)	71 – 98 ^
EoT	Actual EoT	Study day of last dose# (28 days prior to last dose - 7 days post last dose)
Post Treatment	4 weeks (28 days post last dose)	8– 56 post last dose
	12 weeks (84 days post last dose)	57 – 126 days post last dose
	24 weeks (168 days post last dose)	127 – 252 days post last dose
	48 weeks (336 days post last dose)	253 – 420 days post last dose

^values must also be  $\leq$  7 days post last dose

#  $\geq$ study day 2

#### 4.2.3 Handling of missing data

No data will be imputed for any effectiveness or safety analyses except for the analyses of the HCV RNA endpoints and certain PRO endpoints. The discussion of missing data imputation for the PRO endpoints is included in section 4.2.7.2.3.

HCV RNA values will be selected for an RVR, EOTR and SVR analysis based on visit windows as defined in Table 4. When there is no HCV RNA value in a visit window based on defined visit windows, the closest values before and after the window, regardless of the value chosen for the subsequent and preceding window, will be used for the flanking imputation described below. For analysis of RVR, EOT and SVR, if a subject has a missing HCV RNA value at a post-Day 1 visit but with undetectable or unquantifiable (LLoD or LLoQ  $\leq$ 50 IU/mL) HCV RNA levels at both the preceding value and succeeding value, the HCV RNA level will be considered undetectable or unquantifiable, respectively, at this visit for this subject. In addition, if a subject has an

unquantifiable HCV RNA level at the preceding value and an undetectable HCV RNA level at the succeeding value, or vice versa, the HCV RNA level will be imputed as unquantifiable at this visit for this subject.

For analyses of RVR, subjects still missing a value for the visit after flanking imputation will be considered as a failure. For EoTR and SVR analysis, if there is no value in the appropriate window after flanking imputation but there is an HCV RNA value after the window, then it will be imputed into the EoTR or SVR window respectively. Subsequent to this flanking and backward imputation, if the HCV RNA value remains missing at a specific time point, then the subject will be considered as virological failure at this time point (i.e., not undetectable or unquantifiable).

If a subject starts another treatment for HCV, then all HCV RNA values for this subject measured on or after the start date of the new HCV treatment will be excluded from analyses. The subject will be considered a failure for summaries of viral response at all time points after the start of the new HCV treatment.

Due to the non-interventional nature of this study several different methods for determination of the HCV RNA value can be applied. For the purpose of the statistical analysis, a HCV RNA measurement is considered <50 IU/mL,

- if a PCR test was used
- and the test result is undetectable and the LLoD of the test is ≤50 IU/mL or the test result is unquantifiable (i.e. detected but below LLoQ) and the LLoQ is ≤50 IU/mL.

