**Confidential Information**

#### 9.4.1.4 HCV RNA Sample

HCV RNA sample – the following needs to be documented:

- **Quantitative HCV RNA by PCR test**
  - Test name and result in IU/mL
  - Lower limit of detection (LLoD) in IU/mL and lower limit of quantification (LLoQ) in IU/mL
  
- **Qualitative HCV RNA by PCR test**
  - Test name and result (positive/negative)
  - LLoD in IU/mL

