### **9.9 Limitations of the Research Methods**

The limitations of observational studies, such as uncontrolled confounding by lack of randomization, and difficulties to clearly interpret treatment effects in the context of missing data are well known. Their validity can be increased by accurate outcome measurements, documentation of the most common confounders, sufficient length of follow-up and by activities to obtain complete recording of available data as well as by searches for missing key data.

The most important outcome measure in this study is HCV RNA. Missing or unrecorded follow-up HCV RNA data can in particular lead to an underestimation of the real SVR rate as compared to the SVR rate of interventional trials. Highly sensitive and quantitative diagnostic tests are required to measure HCV RNA levels in blood. In an observational study each center will be using its own test – either commercially available or so-called “home-brew” tests – which might change from one visit to the next within a patient data set. The challenge is to accurately and consistently document test properties such as the LLoD and the ILLoQ to put the results into perspective of prior outcomes from

randomized controlled trials with (usually) central laboratory assessments for all trial participants.

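### Read literally, the SAP lets a week-12 negative HCV RNA result with a limit above 50 IU/mL or unrecorded fill the SVR12 window, fail, and block imputation, even when a later qualifying negative exists

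*SAP*

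**What the plan says.** Four rules in the SAP act together on the primary endpoint.

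- **Window assignment (SAP 4.2.2, text below Table 2).** "All recorded HCV RNA values will be assigned to appropriate time points". No condition is placed on the test's LLoD or LLoQ. SAP 4.1.1 and Table 3 set the SVR12 window at 70 to 126 days after the last dose.
- **Trigger for imputation (SAP 4.2.3).** Flanking opens with "When there is no HCV RNA value in a visit window based on defined visit windows, the closest values before and after the window". Backward imputation for SVR applies "if there is no value in the appropriate window after flanking imputation but there is an HCV RNA value after the window". Both need an empty window.
- **What counts as <50 IU/mL (SAP 4.2.3).** It must be a PCR test, and either "the test result is undetectable and the LLoD of the test is ≤50 IU/mL" or the result is unquantifiable with an LLoQ within the same limit.
- **What remains missing (SAP 4.2.3).** If nothing can be imputed, "then the subject will be considered as virological failure at this time point".

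The primary analysis uses all core population patients (SAP 4.2.7.1), so a failure of this kind stays in the denominator.

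Protocol 9.4.1.4 accepts qualitative positive/negative tests and asks for the LLoD. Protocol 9.9 expects each centre to use its own assay, including in-house ones, and adds: "The challenge is to accurately and consistently document test properties such as the LLoD". Protocol 9.7.1 takes the single last measurement at least 70 days after treatment, with no upper bound. The 126-day bound was introduced in the SAP for consistency with other studies.

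**The concern.** A negative result from an insensitive test, or one whose limit was never entered, is a recorded value that does not meet the <50 IU/mL criterion. Taken at face value, the rules count it as a failure, and because the window is no longer empty they also close both imputation routes. A patient who was cleared of virus, and whose later sensitive test shows it, can then be an SVR12 failure only because an extra, less informative test was done at week 12.

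Nothing in the plan suggests that this is intended. The SAP is silent on whether such a result is a value or is missing, so two programmers could follow the same text and report different primary rates. The protocol's last-value rule would have let the later negative decide; the SAP's upper bound removes that.

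**Working it through.** **Step 1: reproduce the plan's own precision figure.** Inputs from SAP 3.2: SVR12 of 95%, n = 620, Wilson score interval, two-sided 95% (z = 1.96).

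Centre = (p + z²/2n)/(1 + z²/n) = (0.95 + 0.003098)/1.006196 = 0.9472.

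Half-width = z·√(p(1−p)/n + z²/4n²)/(1 + z²/n) = 1.96 × √(0.00007661 + 0.00000250)/1.006196 = 0.0173.

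Interval 92.99 to 96.46, width 3.47 points. The SAP states 93.0 to 96.5 and 3.5%, so its figure is reproduced. The rows for n = 590 (width 3.55) and n = 62 (11.77) also agree after rounding.

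**Step 2: apply the rules case by case.** Take a patient with a qualifying negative before the window and at most one result inside it. The LLoDs of 15 (qualifying) and 100 (not qualifying) are illustrative and do not come from the documents.

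| Result at 70–126 days | Value after day 126 | SAP, literal | SAP, result treated as missing | Protocol 9.7.1, last value ≥70 days |
|---|---|---|---|---|
| none | none | failure | failure | failure |
| none | negative, LLoD 15 | success | success | success |
| none | positive | failure | failure | failure |
| negative, LLoD 100 or blank | none | failure | failure | failure |
| negative, LLoD 100 or blank | negative, LLoD 15 | **failure** | **success** | **success** |
| negative, LLoD 100 or blank | positive | failure | failure | failure |

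The reversal occurs in one row: a non-qualifying negative in the window and a qualifying negative afterwards. The earlier negative is not essential, because backward imputation needs only the later value. Treating the result as missing can move a patient only from failure to success, so under the literal reading the bias has one direction, downward.

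**Step 3: illustrate the size.** The share of core population patients in that row is not given in either document. Assume 0.5% to 5%, and start from 589/620 = 95.0% with such results treated as missing.

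| Assumed share | Patients (share × 620) | SVR12, literal reading | Wilson 95% CI |
|---|---|---|---|
| 0% | 0 | 589/620 = 95.0% | 93.0–96.5 |
| 0.5% | 3 | 586/620 = 94.5% | 92.4–96.1 |
| 1% | 6 | 583/620 = 94.0% | 91.9–95.6 |
| 2% | 12 | 577/620 = 93.1% | 90.8–94.8 |
| 5% | 31 | 558/620 = 90.0% | 87.4–92.1 |

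**Step 4: does the sensitivity analysis catch it?** CPSFU membership for SVR12 asks for evaluable HCV RNA data at least 70 days after the last dose, with no upper bound (SAP 4.2.1). The affected patient has a qualifying value after day 126, so belongs to that population however the term is read, and carries the same failure into it. The undefined term matters for a different patient: one whose only result from day 70 on is a non-qualifying negative. That patient is kept as a failure if the result is evaluable; if it is not, the patient drops out unless a safety or efficacy reason applies.

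**The case against.** The strongest reply is that the plan never says such a result is a failure. SAP 4.2.3 lists when a measurement counts as <50 IU/mL; it does not classify the rest. The SAP uses the notion of evaluable HCV RNA data in the CPSFU definition and at the second interim analysis, which fits with treating these results as missing. The list also cannot be exhaustive: read strictly, a quantified 30 IU/mL is neither undetectable nor unquantifiable and would not count as <50 either. This stands, and it makes the point an unresolved ambiguity. It does not resolve it, because the 50 IU/mL condition is attached to the flanking values and not to the trigger that opens imputation, and the term evaluable is never defined.

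Second, the SAP does not say which value is used when several fall in the window, so a second, qualifying in-window result could rescue the patient. This also stands; the point is limited to patients without one.

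Third, the limits are required documentation items, and eCRF checks, queries and investigator sign-off follow (Protocol 9.4.1.4, 9.6.1 and 9.8; SAP 5). These should reduce blank limits. They cannot change an assay whose limit is truly above 50 IU/mL, and no analysis rule covers what is left.

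Fourth, refusing credit to a test that cannot establish <50 IU/mL is defensibly conservative, and Protocol 9.9 already warns that missing or unrecorded data can understate SVR. That justifies not counting the insensitive test as a success. It does not justify letting that test cancel a later sensitive one which the SAP would accept had the week-12 sample not been taken.

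**Conclusion.** The point holds in conditional form. On a literal reading, a patient with a non-qualifying negative at 70 to 126 days, no other qualifying result in that window, and a qualifying negative after day 126 is an SVR12 failure, while the same patient untested at week 12 is a success. No other passage in either document resolves this. Under that reading the primary rate is biased downward. The size is unknown: 3 to 31 of 620 patients, or 0.5 to 5 points, follows from an assumed share of 0.5% to 5% and from nothing in the documents. For scale, the planned full interval width is 3.5 points.

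A reader might infer more than the documents support:

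- **That any patient with a weak negative fares worse than an untested one.** Without a later qualifying value, both fail.
- **That the SAP has settled on failure.** It leaves the status of such results open.
- **That the exploratory regression term for type of treating institution is contaminated.** Protocol 9.9 says tests vary by centre, but nothing links assay limits to institution type.

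**What to change.** Add to SAP 4.2.3, ahead of the imputation rules, wording to this effect:

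*A negative or unquantifiable result with LLoD/LLoQ above 50 IU/mL, or with the limit neither recorded nor derivable from the recorded test name, is not evaluable. It does not occupy a window and is skipped as a preceding, succeeding or carried-back value. Another evaluable value in the window is used first, then flanking, then backward imputation. If none exists, the patient remains a failure.*

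Define evaluable in the CPSFU criteria of SAP 4.2.1 in the same way, and report the number of non-evaluable results in the SVR12 window. In the same edit, correct the cross-reference in SAP 4.2.3, which points to Table 4 although the HCV RNA windows are in Table 3.

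The cost is one paragraph, one derivation and a look-up of assay limits by test name. The look-up may fail for in-house tests, whose results then stay non-evaluable. The rule remains conservative: success still needs a qualifying result from another sample, and positive results are untouched. The small downside is that some SVR12 outcomes will rest on neighbouring samples, as the plan already accepts for untested patients. Response rates have already been tabulated at interim analyses, so the rule should be fixed in writing before the final analysis.
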